7.9 Lost to Follow-up Subjects

Every attempt will be made to have all subjects complete the follow-up visit schedule. A subject will not be considered lost to follow-up unless efforts to obtain compliance are unsuccessful. At a minimum, the effort to obtain follow-up information will include three attempts to make contact via telephone or email and if unsuccessful, then a certified letter from the Investigator will be sent to the subject's last known address. In general, the study Site Coordinator should attempt to contact the subject as soon as possible after each missed visit to reschedule the visit.

8 RISK / BENEFIT ANALYSIS

8.1 Benefits

Possible benefits of the use of the Levita Magnetic Surgical System and Robotic Platform are a reduction in the number of surgical incisions needed to perform the surgery, with associated reduction in post-operative pain and scarring, a shorter length of stay in the hospital, faster recovery, and reduced intraoperative labor required.

8.2 Risks

There are risks associated with use of the Levita Magnetic Surgical System and Robotic Platform including:

- Electromagnetic field incompatibility or interference
- Malfunctioning of the device
- Breakage of the device
- Allergic reaction related to the device
- Abdominal wall/cavity/tissue and/or organ injury or damage (e.g. inflammation, redness)
- Infection
- Tissue damage, including hematoma, bleeding or petechiae
- Vascular injury
- Gastro-intestinal injury
- Organ perforation
- Need for extended surgery

- Additional surgical intervention due to any of the above factors (includes reoperation)

These adverse events do not include all adverse events, which occur with surgery in general, but are important considerations particular to laparoscopic instrumentation.

8.3 Minimization of Risk and Monitoring Procedures

Levita Magnetics has attempted to mitigate risks as much as possible through product design and development of the MSS which included *in vivo* performance testing, human factors testing, non-clinical performance testing, clinical testing of the MSS in other surgical procedures, biocompatibility testing, sterilization validation, reprocessing validation and shelf life validation. Additionally, careful labeling, IFU and training are provided as detailed below for the MSS and LRP.

Risks will be further mitigated through selection of qualified physicians with competence in minimally invasive surgery, appropriate training, and study monitoring.

- Investigators who participate in the study will be experienced and skilled in laparoscopic surgical techniques. Additionally, Investigators, in conjunction with the investigational site, will have adequate resources for participation in a clinical study.
- The study has been designed to ensure treatment and follow-up of subjects are consistent with current medical practice.
- Each Investigator will ensure oversight and approval of the study by the Ethics Committee (EC) prior to initiation of the clinical study at his/her investigational site.
- The Investigator and study personnel will be trained on the clinical protocol.
- All Investigators who have not previously used the Levita MSS will undergo training with MSS prior to first use during the clinical study.
- All Investigators and operating room support personnel will be provided with a detailed IFU during training and as a reference for review as needed.
 - The IFU details appropriate safety zones for use of the Magnetic Controller in an OR setting and considerations for users of a product with a strong magnet.
- Study personnel are also trained with and receive a “Magnetic Surgery Screening Checklist” and Operating Room (OR) signage to ensure safe use of the system for subjects and users.
- Subjects will be carefully evaluated against the inclusion/exclusion criteria prior to entering the clinical study to ensure that their diagnosis and medical status are appropriate for participation in the clinical study.

- Subjects will be monitored up to the 30-day follow-up visit as defined in the study protocol. The follow-up visit will be with an Investigator to monitor the subjects' status.
- A study Investigator will evaluate the subject for any adverse events potentially related to the device.
- Levita Magnetics or its designee may conduct monitoring visits at the investigative sites at the initiation of the study and periodically throughout the study to evaluate protocol compliance and to determine if there are any issues that may affect the safety or welfare of the subjects.

9 STATISTICAL SECTION

9.1 Statistical Methods

This study is not planned to provide statistical data but to provide initial outcomes for safety and feasibility of the LRP used with the MSS.

Descriptive tables may be produced for baseline characteristics including demographics and medical history and for study outcomes.

9.2 Sample Size Justification

This is a single-arm, multi-center, investigational study to understand the safety and feasibility of the use of the LRP with the MSS. A sample size of 100 subjects was planned to allow use of the system in a number surgeons and a number of different types of laparoscopic procedures. It is expected that enrollment of 100 subjects will provide appropriate information regarding the safety and feasibility of the LRP and MSS in laparoscopic procedures.

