Clinical Evaluation of the Levita Robotic Platform

Protocol Number: CP007
Revision: A
January 12, 2021

Sponsor: Levita Magnetics
[name]
Title: CEO and Founder
Email: [contact]
[contact]

Sponsor Signature: _____

Sponsor Name: [name]

CONFIDENTIALITY STATEMENT

This study is confidential in nature. All information related to this study is considered proprietary and should not be made available to those not directly involved in this study. Authorized recipients of this information include Investigators and co-Investigators, other health care personnel necessary to conduct the study, and Clinical Investigation Ethics Committees and Institutional Review Boards. The personnel provided with data from this study are hereby informed of its confidential and proprietary nature. Release of these data to individuals other than those listed above requires the prior written permission of Levita Magnetics.

PROTOCOL REVIEW PAGE

STUDY TITLE: Clinical evaluation of the Levita Robotic Platform
PROTOCOL: CP007
REVISION: A

Investigator's Statement: I agree to conduct this clinical study in accordance with the design and specific provisions of this protocol; modifications to the study or protocol are acceptable only with a protocol amendment approved by the Study Sponsor and Ethics Committee (EC) if required. I agree to await EC approval for the protocol and informed consent before initiating the study, to obtain informed consent from subjects prior to their enrollment in the study, to collect and record data as required by this protocol and case report forms, submit all reports as required by this protocol, provide the requested financial information, and to maintain study documentation for the period of time detailed in this protocol.

Investigator Signature	Date of Signature
Investigator Name:	

Protocol Synopsis

Title:	Clinical Evaluation of the Levita Robotic Platform
Study Objective:	The purpose of this study is to evaluate the safety and feasibility of the Levita Robotic Platform (LRP) used with the Levita Magnetic Surgical System (MSS).
Study Design:	Prospective, multi-center, single-arm, open label study designed to assess the safety and feasibility of the use of the Levita Robotic Platform with the Levita Magnetic Surgical System in laparoscopic procedures.
Enrollment Size and Number of Sites:	Up to 100 subjects in up to 5 clinical sites in Chile

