6 STUDY DESIGN

6.1 Overview

This feasibility study is a prospective, multi-center, single-arm, open label study designed to assess the safety and feasibility of the use of the Levita

Robotic Platform with the Levita Magnetic Surgical System in laparoscopic procedures.

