6.2 Sample Size and Number of Centers

The study will be conducted at up to five (5) clinical sites with a target maximum of 100 subjects in which the Robotic Platform and Levita Magnetic Surgical System is used for laparoscopic procedures.

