7 STUDY PROCEDURES

7.1 Subject Eligibility, Pre-Screening, and Exclusions

All subjects presenting for elective laparoscopic procedures are potential candidates, and will be screened for eligibility. Study clinicians will select subjects based on knowledge/experience. A Screening/Enrollment Log will be provided to the study sites to maintain a cumulative tracking of all screened subjects.

Subjects must meet all study entrance criteria for enrollment in the clinical study. Reasons for screening failure(s) will be documented.

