7.1.1 Inclusion Criteria

Subjects must meet ALL of the following inclusion criteria to be eligible for participation in the study:

1. Subject is at least 18 years of age
2. Subject is scheduled to undergo elective laparoscopic procedure
3. Subject signs a written Informed Consent Form (ICF) to participate in the study prior to any study required procedures

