7.2 Enrollment and Written Informed Consent

Patients who pass initial pre-screening will be asked to sign the Informed Consent Form (See **Appendix 1**) before any study-specific tests or procedures are performed. The Investigator will inform the potential subject of the elements of the clinical study, including risks, potential benefits and required follow-up procedures, prior to obtaining the potential subject's informed consent. Enrollment may be non-sequential per the discretion of the study surgeon.

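### Does the breadth rationale for 100 subjects in section 9.2 need enrolment rules on the mix of operations and surgeons?

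*Combined protocol and SAP*

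**What the plan says.** Section 9.2 gives one reason for the sample size: 100 subjects were "planned to allow use of the system in a number surgeons and a number of different types of laparoscopic procedures". It then expects that this enrolment "will provide appropriate information regarding the safety and feasibility of the LRP and MSS in laparoscopic procedures". That second sentence asserts adequacy and adds no criterion.

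The rules that shape the mix are these:

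- **Size and sites.** The Synopsis has "Up to 100 subjects in up to 5 clinical sites in Chile", and section 6.2 has "up to five (5) clinical sites with a target maximum of 100 subjects". Both are ceilings.
- **Design.** Section 6.1 describes a "prospective, multi-center, single-arm, open label study", which implies at least two sites.
- **Operation.** Section 7.1.1 requires only this: "Subject is scheduled to undergo elective laparoscopic procedure".
- **Selection.** Section 7.1: "Study clinicians will select subjects based on knowledge/experience". Section 7.2: "Enrollment may be non-sequential per the discretion of the study surgeon".

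Section 9.1 states that the study is meant to give initial safety and feasibility outcomes, not statistical data. Descriptive tables of baseline characteristics and outcomes are optional, and no breakdown is named. The intra-operative data list in section 7.4 has a general entry for device and procedure observations and a video of the whole procedure. It does not name the type of operation or the operating surgeon.

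**The concern.** Breadth is the only reason offered for 100, yet every rule that governs breadth is either a maximum or a matter of discretion. No minimum number of surgeons or operation types is set, nor any minimum per type or cap on one type. Surgeons who favour familiar operations could fill most of the study with one of them without breaking an eligibility or enrolment rule.

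The objective in section 4 is worded for laparoscopic procedures in general, whereas section 1.1 cites evidence on the magnetic system (MSS) operation by operation: gallbladder retraction, and liver mobilization in bariatric surgery. If pooled feasibility, conversion and device-event figures came mainly from one operation, they would say little about the others. Operative time, length of stay and number of surgeons also depend on the operation, so their pooled values would shift with the mix. Operations that were never enrolled cannot be recovered at analysis.

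**Working it through.** **1. The plan's own figure.** The 100 cannot be re-derived. The documents give no error rate, power, event rate, precision target, or number of surgeons or operation types. There is nothing to reproduce and no figure to contradict.

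**2. What a lopsided mix would leave unknown.** The documents give no mix, so the splits below are assumptions. With no events in n subjects, the exact two-sided 95% upper limit is 1 − 0.025^(1/n).

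| Group | n | Upper limit |
|---|---|---|
| All subjects | 100 | 3.6% |
| Dominant operation in a 95:5 split | 95 | 3.8% |
| Remaining operations in a 95:5 split | 5 | 52.2% |
| One operation with 10 cases | 10 | 30.8% |
| One of five equal types | 20 | 16.8% |

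**3. What quotas could buy.** The chance of seeing an operation-specific problem at least once is 1 − (1 − p)^n.

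- Assumed p = 10%: n = 28 gives 94.8% and n = 29 gives 95.3%. Three groups of 29 use 87 of the 100 subjects.
- Assumed p = 20%: n = 13 gives 94.5% and n = 14 gives 95.6%. Seven groups of 14 use 98.
- At p = 10%, the problem is missed with probability 0.9^10 = 34.9% in 10 cases and 0.9^5 = 59.0% in 5.

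The rates and the 95% target are chosen for illustration; the plan adopts neither.

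**4. How far case mix could move a pooled result.** Pooled success is m·s1 + (1 − m)·s2, where m is the share in the familiar operation.

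- With assumed s1 = 99% and s2 = 80%: 97.1% at m = 0.9, 89.5% at m = 0.5 and 81.9% at m = 0.1, a range of 15.2 points.
- With assumed s1 = 98% and s2 = 85%: 96.7%, 91.5% and 86.3%, a range of 10.4 points.

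Each range is 0.8 × (s1 − s2), that is 0.8 × 19 and 0.8 × 13. It restates the assumed gap between operations and is not evidence that one exists.

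**5. The rationale against the rules.** Section 9.2 says the number is meant to allow use across surgeons and operations. Up to five sites, any elective laparoscopic operation and up to 100 subjects do allow it. The sentence describes capacity; it does not promise a particular mix. A study of 100 identical operations would depart from the plan stated in 9.2, even though it met every entry criterion. A heavily unbalanced study would not. The sections can therefore be read together without contradiction.

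**The case for a change.** The strongest argument for a change is that the mix is settled at enrolment, while the remedy costs little. Two or three sentences could say that the mix is surgeon-selected and limit the conclusion to operations with enough cases, with no extra subjects and no loss of surgical discretion. It is also true that no by-operation table is promised and that section 7.4 does not list operation or surgeon.

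The textual observation stands: nothing in the sections on eligibility, enrolment, design or statistics sets a floor or a cap. Three things weaken the step from there to a defect.

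- The low-cost remedy changes no enrolment rule. If it is sufficient, the issue is how results are described. Section 9.1 does not require pooled-only reporting, and a breakdown by operation needs no amendment. The operation performed can be expected in the surgical record and is visible on the procedure video.
- The remedy that does act on enrolment, quotas or caps, has a real price. It restricts case choice in early use of a device and may slow the planned 12 months. Seven groups of 14 would leave 2 spare subjects under a maximum of 100, while exclusion 5 in section 7.1.2 can apply after surgery has begun.
- The operation-specific evidence in section 1.1 concerns the MSS. The new element is the robotic platform (LRP), which replaces the support arm. Feasibility outcomes 1 and 2, on coupling and movement and on the camera view, would be new information even in cholecystectomy. The documents do not show that platform performance differs by operation.

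**Conclusion.** No change to the plan is needed. The rationale in section 9.2 is loosely worded and no rule enforces the mix, but it describes what the sample makes possible, and the design does make it possible. No stated figure, rule or analysis is wrong. What is left is missing detail that an analyst would sensibly fill: count the cases by operation and surgeon, show outcomes by operation beside the overall figures, and word the conclusion for the operations actually performed. Quotas are a trade-off that the sponsor may fairly decline in a descriptive single-arm feasibility study.

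On size, a 95:5 split with no events would leave an upper limit of 52.2% for the 5 minority cases, against 3.6% overall. That is a reason for restraint in the report's wording; it does not breach any aim the plan sets. The 15.2-point and 10.4-point case-mix ranges depend entirely on assumed success rates. The conclusion rests on reading section 9.2 as enabling, and on the operation being identifiable from study or surgical records; the case report forms are not reproduced in the document.

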10 DATA MANAGEMENT

10.1 Data Collection

Data will be collected on paper case report forms (CRF) supplied by the Sponsor. The Site Principal Investigator is responsible for the accuracy and completeness of all study documentation.

Corrections to the CRF must be made by drawing a single line through the incorrect data, entering the correct data beside the incorrect entry, then initialing and dating the correction. Incorrect data must not be obscured. The use of pencil, erasable ink, or correction fluid on CRFs is prohibited. All fields must be completed, e.g. if the item was not done, mark "N/D". If the item is not applicable to an individual case, mark the field "N/A".

CRFs will be printed on 3-part NCR paper (or equivalent) so that both the site and monitor/Sponsor will have copies of the CRFs. One of the three copies may be sent to the Sponsor for remote monitoring. Any other subject

information sent to the Sponsor must be redacted of personal identification information.

A unique study number will be assigned to each subject. All information recorded on the CRF about the subject will be recorded with the study number on it. The main database will contain only the study number to identify the subject. The code with subject name and study number will be maintained in a secured designated location at the site and will be inspected by study monitors and auditors. Any computerized data will be password protected.

Levita Magnetics or its designee will be responsible for database design and management for this study.

10.2 Data Processing

Prior to data entry, monitoring, as detailed below, may be completed. In association with data entry, the data will be reviewed for further inconsistencies or incongruities. If warranted, a data clarification form or communication will be used to query the Investigator.

11 MONITORING AND QUALITY CONTROL PROCEDURES

11.1 Control of Systemic Error/ Bias

Clinical monitors may verify subject data and ensure compliance with Good Clinical Practices (GCPs), clinical protocol and other study requirements.

11.2 Monitoring and Auditing

Monitoring visits to the clinical sites may be made periodically during the study, to ensure that all aspects of the current, approved protocol/amendment(s) are followed.

Prior to the enrollment of any subject in this study, site study personnel will be trained to the protocol and the device including the IFU. Additionally, the procedure for obtaining informed consent and the procedure for reporting adverse events will be reviewed.

The Monitor will ensure through personal contact with the Investigator and site personnel that the members of the clinical staff clearly understand and accept the obligations incurred in this investigation, and that these obligations are being fulfilled throughout the study. Specifically, the Monitor will interact with the site via telephone contact and potentially periodic on-site visits to ensure that:

- Qualified subjects are appropriately consented
- Regulatory and study documents are complete and current
- The protocol is appropriately followed

- Protocol amendments have been approved by the EC and the hospital director (as applicable) and the Sponsor has received the approval in writing
- Accurate, complete, and current records are maintained for all subjects
- Source data verification may be undertaken to ensure the information recorded and submitted to the Sponsor is representative of the subject record and other supporting documentation
- Inconsistent and incomplete data are addressed and resolved
- Accurate, complete, and timely adverse event reports are being made to the Sponsor
- Investigational devices are properly stored, dispensed, and accounted for

The Investigator or designee must, upon request, provide to the Monitor or regulatory authority the necessary study records for a thorough review of the study's progress. These records include, but are not limited to, case report forms and original documents and records such as hospital and clinic charts, consent forms, laboratory records, and pharmacy dispensing records.

The Monitor will provide a written report to the Sponsor after each on-site visit. The report will identify the personnel participating in the visit, the activities performed, any protocol deviations, and any action items/corrective actions identified.

If compliance problems or protocol deviations are noted, the Sponsor will recommend corrective action. If the response from the Investigator is not adequate, the Sponsor will terminate the site's participation in the study and notify the regulatory authorities (if applicable).

The study may also be subject to a quality assurance audit by the Sponsor or its designees, as well as inspection by appropriate regulatory authorities.

It is important that the Investigator and relevant study personnel are available during the monitoring visits and possible audits and that sufficient time is devoted to the process.

11.3 Device Accountability

Access to investigational devices shall be controlled and used only in the clinical investigation and according to the protocol.

The Sponsor shall keep records to document the physical location of all investigational devices from shipment (or hand-carried) to the sites until return or disposal.

The site Principal Investigator or an authorized designee shall keep records documenting the receipt, use, return, and disposal of the investigational device, which shall include:

- The date of receipt
- Identification of each investigational device (lot number)
- The date of use
- Subject study identification number
- Date of return of unused or malfunctioning investigational devices, if applicable
- Date of disposal, if applicable

The Investigator must explain in writing the reasons for any discrepancy noted in device accountability.

12 ADVERSE EVENTS

12.1 Definitions

12.1.1 Adverse Event (AE)

AEs are any untoward medical occurrence, unintended disease or injury, or untoward clinical signs (including abnormal laboratory findings) in which subjects, users or other persons, whether or not related to the investigational medical device. This definition includes events related to the procedures involved. For users or other persons, this definition is restricted to events related to investigational medical devices.

All adverse events, regardless of relationship to the device, must be recorded on the case report forms provided. Adverse events that occur during this study should be treated by established standards of care.

Adverse events shall be assessed and documented at the time of the procedure and at all study follow-up visits. Each Investigator shall provide source documentation as requested by the Sponsor to facilitate reporting and adjudication of these events.

